#### **12.2.2 Other Efficacy Endpoints**

The effect of the length of time (minutes) between key events on the primary endpoints will be analyzed using logistic regression with time as the explanatory variable. The time intervals considered are time from onset of symptoms to first dose of investigational product and time from first dose of investigational product to ECG/angiography. Separate analyses will be conducted for each time interval and each primary endpoint.

Categorical endpoints will be compared using Chi-Square tests. This includes complete ( $\geq 70\%$ ) ST-segment elevation resolution at 60 minutes post PCI, TIMI flow grade 3 at end of procedure, Thrombotic bail-out with GPIIb/IIIa inhibitors at initial PCI and both composite endpoints.

The ordinal TIMI myocardial perfusion grade at angiography will be compared using the Cochran-Mantel-Haenszel test with modified ridit scores.

Corrected TIMI frame counts will be compared using analysis of variance (ANOVA).

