**Objectives**

Primary objectives	Outcome variables
To assess the efficacy of pre-hospital vs. in-hospital initiation of ticagrelor therapy by comparing the percentage of patients reaching the co-primary endpoint of TIMI flow grade 3 of MI culprit vessel at initial angiography or a $\geq 70\%$ ST-segment elevation resolution pre-PCI.	Co-primary endpoint is the percentage of patients reaching TIMI flow grade 3 of MI culprit vessel at initial angiography or a $\geq 70\%$ ST-segment resolution pre PCI

Secondary objectives	Outcome variables
To compare the efficacy of pre-hospital vs. in-hospital initiation of ticagrelor therapy by assessing the following endpoints:	

1.	Composite of death, MI, stroke, urgent revascularization and acute stent thrombosis during 30 days of study.	Percentage of patients in the following: composite of death, MI, stroke, urgent revascularization and acute stent thrombosis during 30 days of study .
2.	Composite of death, MI, urgent revascularization during 30 days of study	Percentage of patients in the following: composite of death, MI, urgent revascularization during 30 days of study
3.	Acute stent thrombosis during 30 days of study	Percentage of patients presenting an acute stent thrombosis episode during 30 days of study
4.	Thrombotic bail-out with GPIIb/IIIa inhibitors at initial PCI	Percentage of patients receiving thrombotic bail-out with GPIIb/IIIa inhibitors at initial PCI
5.	Complete ( $\geq 70\%$ ) ST-segment elevation resolution at 60 min post-PCI	Complete ( $\geq 70\%$ ) ST-segment elevation resolution at 60 min post-PCI
6.	Corrected TIMI frame count (cTFC) at angiography, pre and post PCI.	Corrected TIMI frame count (cTFC) at angiography, pre and post PCI
7.	TIMI myocardial perfusion grade (TMPG) at angiography, pre and post PCI.	TIMI myocardial perfusion grade (TMPG) at angiography, pre and post PCI
8.	Time–relationship (from symptom onset to 1st dose intake) on each co-primary	Time from symptom onset to 1st dose intake correlated to TIMI flow grade 3 of MI culprit vessel at initial angiography and on $\geq 70\%$ ST-segment elevation resolution pre-PCI
9.	Time–relationship (from 1st dose intake to ECG/ angiography) on each co-primary	Time from first dose intake to ECG correlated to $\geq 70\%$ ST-segment elevation resolution pre-PCI and time from randomization to initial angiography correlated to TIMI flow grade 3 of MI culprit vessel

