## **2.2 Secondary objectives**

To compare the efficacy of pre-hospital vs. in-hospital initiation of ticagrelor therapy by assessing the following endpoints:

- Composite of death, MI, stroke, urgent revascularization and acute stent thrombosis during 30 days of study
- Composite of death, MI, urgent revascularization during 30 days of study
- Acute stent thrombosis during 30 days of study
- Thrombotic bail-out with GPIIb/IIIa inhibitors at initial PCI
- Complete ( $\geq 70\%$ ) ST-segment elevation resolution at 60 min post-PCI
- Corrected TIMI frame count (cTFC) at angiography, pre and post PCI.
- TIMI myocardial perfusion grade (TMPG) at angiography, pre and post PCI.
- Time–relationship (from symptom onset to 1st dose intake ) on each co-primary
- Time–relationship (from 1st dose intake to ECG/ angiography) on each co-primary
- TIMI flow grade 3 at end of procedure.

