### **5.5.2 Doses and treatment regimens**

At Visit 1 (randomisation), eligible patients will be randomly assigned to one of two treatment groups:

- 2 tablets of ticagrelor (loading dose) taken in the ambulance followed by 2 tablets of matching placebo in the hospital, taken orally.

Or

- 2 tablets of matching placebo taken in the ambulance followed by 2 tablets of ticagrelor (loading dose) in the hospital, taken orally.

After that initial double blind period, all patients will continue on active ticagrelor 90 mg BID and will be followed in study for 30 days post randomisation.

Randomization will be managed by the ambulance personnel by opening the patient pack and administering the first dose of study medication. The second dose will be taken at Visit 2 before undergoing ECG and angiography

Subsequent maintenance doses should be taken morning and evening, at approximately 12-hourly intervals, for the remainder of the treatment period.

Study medication can be taken with or without food. Study medication should not be altered (eg, crushed, put in another vehicle) and should not be given by nasogastric tube or other routes.

The treatment for the entire study will be packaged so that it will follow the patient from the ambulance to the hospital. Individual patient treatment is defined as the double blinded loading dose (2x2 tablets), a bottle of ticagrelor 90 mg containing 64 tablets (30 days of active treatment + 2 days overage), and the Informed Consent Forms will be provided to each ambulance. Each treatment will be clearly identified.

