### **Visit 2: will occur in Cath Lab of the hospital**

The Cath Lab's personnel will check that the individual patient study medication is present, the Informed Consent Form is signed, the source paper CRF or equivalent is completed and 2 print outs of the ECG done in pre-hospital settings are present.

If only the short form of the Informed Consent Form is signed then the full Informed Consent Form will be obtained as soon as the clinical situation allows it and before first dose intake of active ticagrelor 90 mg. If a patient is unable to read and sign due to critical condition, the full Informed Consent Form will be signed as soon as the clinical situation allows it, please refer to section 8.4.

In-hospital treatment must be given in the Cath Lab, before the ECG and pre-PCI angiography.

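### The secondary time-relationship models contain no treatment term, so they describe an overall time association but not whether the effect of pre-hospital initiation varies with time

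*Protocol*

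**What the plan says.** Section 2.2 of the protocol opens its list of secondary objectives with "To compare the efficacy of pre-hospital vs. in-hospital initiation of ticagrelor therapy by assessing the following endpoints". Two of the ten items are time relationships on each co-primary endpoint. Section 12.2.2 defines the intervals as "time from onset of symptoms to first dose of investigational product and time from first dose of investigational product to ECG/angiography". The effect of these intervals "on the primary endpoints will be analyzed using logistic regression with time as the explanatory variable", and "Separate analyses will be conducted for each time interval and each primary endpoint". Two intervals and two endpoints make four models. Section 12.1.1 places all efficacy endpoints in the modified ITT set, which contains both arms.

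Section 5.5.2 describes the in-hospital arm as "2 tablets of matching placebo taken in the ambulance followed by 2 tablets of ticagrelor (loading dose) in the hospital, taken orally". The Visit 2 text adds: "In-hospital treatment must be given in the Cath Lab, before the ECG and pre-PCI angiography".

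The synopsis table of objectives describes the outcome for these items only as a correlation of time with each endpoint. For TIMI flow it names "time from randomization to initial angiography correlated to TIMI flow grade 3 of MI culprit vessel", whereas sections 2.2, 11.1 and 12.2.2 start that interval at the first dose.

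**The concern.** The first-dose interval does not mean the same thing in the two arms. For a pre-hospital patient, first dose to ECG or angiography is time on ticagrelor. For an in-hospital patient it is time since placebo, with the active loading dose taken in the Cath Lab shortly before the assessment. A slope fitted across both groups mixes any drug-exposure effect with whatever transport time and spontaneous reperfusion contribute in everyone.

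The rationale in section 1.3 is that earlier treatment brings greater benefit. The trial can address this by asking whether the between-arm difference grows with the interval. A model without treatment does not estimate that quantity. If its slope were reported under the comparative objective, it could be taken as evidence for or against pre-treatment time when it is neither.

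**Working it through.** **The plan's own figure.** The protocol gives no number for the time analyses. The sample size used to scale the simulation does reproduce. With 15% versus 21%, two-sided alpha 2.5% and 80% power:

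n = [2.2414 × √(2 × 0.18 × 0.82) + 0.8416 × √(0.15 × 0.85 + 0.21 × 0.79)]² / 0.06² = 778.1, rounded up to 779 per group; 1558/0.88 = 1770.5, against 1770 stated. This is not in dispute.

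**What each model estimates.** Let Z = 1 for pre-hospital, 0 for in-hospital, and t = time.
- As written: logit P = a + b·t. At a given t both arms have the same fitted probability, so there is no between-arm quantity to report.
- With treatment: logit P = a + d·Z + b·t + g·Z·t. The treatment log-odds ratio at time t is d + g·t, and g says whether it changes with time.

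**What the pooled slope becomes.** With the same time distribution in both arms, b is approximately the average of the arm slopes weighted by p(1−p). With the protocol's ST-resolution rates, 0.21 × 0.79 = 0.1659 and 0.15 × 0.85 = 0.1275, so the weights are 0.565 and 0.435. For arm odds ratios of 1.5 and 1.0 per 30 min, exp(0.565 × ln 1.5) = exp(0.229) = 1.26.

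Simulation agrees: 779 per arm, 1000 runs per scenario, rates 21%/15%, tests at 5%. The interval is an assumption not found in the protocol: normal, mean 50, SD 20 min, limited to 10–120, the same in both arms.

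| True OR per 30 min, pre / in | Pooled OR | Pooled significant | Interaction ratio | Interaction significant |
|---|---|---|---|---|
| 1.5 / 1.0 | 1.26 | 63% | 1.50 | 51% |
| 1.25 / 1.25 | 1.25 | 59% | 1.00 | 4.4% |
| 1.0 / 1.5 | 1.20 | 42% | 0.67 | 50% |
| 1.5 / 0.67 | 1.06 | 10% | 2.25 | 97% |

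The first two rows are indistinguishable in the pooled column. The last row is an extreme case shown for contrast; nothing in the protocol suggests opposite slopes. With a common slope of 1.2, the pooled odds ratio is also 1.20 whether the arm rates (pre/in) are 21/15, 18/18 or 15/21%, so it carries no information on which arm does better.

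**Power of the interaction, checked by formula.** The SD in 30-min units is 20/30 = 0.667, with variance 0.444. SE(g) = √[1/(779 × 0.1659 × 0.444) + 1/(779 × 0.1275 × 0.444)] = 0.200. Then ln 1.5/0.200 = 2.03, and power is Φ(2.03 − 1.96) = 53% before limiting the interval to 10–120 min, against 51% simulated.

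**How often the pooled slope is significant with no drug effect.** A second set-up used 814 per arm (885 × 0.92, the protocol's 8% angiographic dropout), 17% response, and an assumed gamma interval with shape 4 and scale 12 min (mean 48). The pooled model was significant in 18%, 48% and 96% of runs for common slopes of 0.03, 0.05 and 0.10 log-odds per 10 min. The formula gives SE = 1/√(1628 × 0.17 × 0.83 × 5.76) = 0.0275, where 5.76 is the variance in 10-min units (4 × 12² = 576 min²). Power is then about 19%, 44% and 95%. These figures are power for a time association that was built into the data.

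**Start of the interval.** Section 5.5.2 has the ambulance crew randomise by opening the pack and giving the first dose, and section 5.2.1 has that dose follow at once. Randomisation and first dose nearly coincide, so the synopsis discrepancy has little numerical effect.

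**The case against.** The strongest reply is that the model suits its own outcome definition. The synopsis asks only how time correlates with each endpoint, and section 12.2.2 speaks of the effect of time. The comparative wording is a heading shared by ten items, and the between-arm question on both co-primaries is answered by the chi-square tests in section 12.2.1. This stands in part: a pooled slope is a legitimate description of an overall association. It still does not serve the comparative objective above it.

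A second reply is that the protocol says neither that time is the sole predictor nor, in words, that the arms are combined, and that section 12 leaves further detail to the statistical analysis plan. That is correct. The combination is inferred from the split by interval and endpoint only, in an analysis set holding both arms. But time is named as the explanatory variable, so this is a stated specification rather than an open one. The provision in section 12.2 for results by treatment group and overall concerns descriptive summaries.

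Third, the placebo problem bears mainly on the second interval. Onset to first dose ends when dosing starts and is essentially a pre-treatment characteristic recorded alike in both arms, although it is time to ticagrelor in only one of them.

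A reader might infer that the planned model produces false positives at a rate near 96%. The documents do not support that. The rate depends on an assumed slope, falls to about 18% for a smaller one, and counts detections of a real time association. It misleads only if the slope is called a drug effect, and section 12.2.2 does not call it one.

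**Conclusion.** The point holds as a mismatch between a stated secondary model and the comparative objective it sits under. As written, the model has no treatment parameter and so cannot show whether the effect of pre-hospital initiation varies with time. This follows from the form of the model and needs no simulation. The simulated sizes rest on assumed slopes and interval distributions and should be quoted only as ranges.

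It would go too far to call the time analyses uninformative or the trial's conclusions at risk. These are secondary analyses outside the Holm procedure; the co-primary tests and the sample size are untouched. The synopsis discrepancy on where the TIMI interval starts is clerical.

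**What to change.** For each endpoint and each interval, fit logistic regression with treatment, time and treatment-by-time. Report the interaction and the treatment effect across the range of observed times, with confidence intervals. If a slope over both arms is kept, label it a descriptive association. Fitting each arm separately would remove the mixing but would give no formal between-arm test.

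State that the interaction is exploratory. Its power is modest (about 51% for a 1.5-fold ratio of odds ratios per 30 min under the assumed interval), so a non-significant result would not show that the treatment effect is constant over time.

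Align the synopsis outcome for TIMI flow with the first-dose start used in sections 2.2, 11.1 and 12.2.2.

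The cost is wording in section 12.2.2 and the synopsis, carried into the analysis plan before database lock. Randomised arm and the onset, dose, ECG and angiography times are already available, so no new data are needed.

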### **12.2.3 Bleeding Events**

Endpoints will be compared between treatment groups in the Safety Population using Chi-Square testing.

Statistical testing of bleeding events will not be considered confirmatory as no pre-specified hypothesis has been made.

### **12.2.4 Other safety data**

Adverse events (AEs) will be summarized by system organ class and preferred term using MedDRA. Summaries will be presented by treatment groups using descriptive statistics. Specific more detailed analyses of dyspnoea and bradycardic events will be performed. All AEs related to bleeding events will be summarized separately.

Safety laboratory parameters and transfusion of blood products will be displayed by descriptive statistics with the change from baseline when appropriate.

### **12.2.5 Interim analyses**

No interim analyses are planned for this study.

## **12.3 Determination of sample size**

Since, based on multiplicity procedure, the initial significance level is 2.5%, the sample size calculation will be based on a significance level of 2.5% and 80% power. Sample size calculations were derived using nQUERY7.

The sample size for the two co-primary endpoints is derived from the ST Resolution hypothesis. However, the study is enough powered for the 2 criteria when considering the table below.

The ST segment deviation was previously studied in On Time2 study (Van't Hof Aw et al 2008), where complete ST resolution occurred in 20.7% of patients in the pre-hospital GP I Ib/IIIa group versus 15.4% in the non GP I Ib/IIIa group, all patients receiving a clopidogrel loading dose. This last number, corresponding to an in-hospital group was confirmed in Assent 4 PCI study where electrocardiographic reperfusion was shown in 14.9% of patients.

Based on this data, it is hypothesized that 15% of patients in the in-hospital group will achieve complete ST elevation resolution versus 21% in the pre-hospital group (absolute difference of 6%). Taking into account a significance level of 2.5%, 779 evaluable patients are required in each treatment group to have 80% power using a two group chi squared test of equal proportions. Assuming a 12% dropout for invaluable or missing ECG criteria, a total of 1770 patients are required to be enrolled in the study to assess the ST segment elevation resolution difference.

To insure the sample size is adequate for the analysis of the co-primary endpoint TIMI Grade at initial angiography, values ranging from 15-27% were reported in various studies. Clinicians agreed that a 30 to 35% relative difference between the 2 groups is clinically relevant. In order to hypothesize on the various degree of angiographic reperfusion expected the following table was created to show a range of hypothesis and the related sample size. A statistical difference can be shown for the highlighted hypothesis (in bold) in the table. Dropout rate at initial angiography is assumed to be low, and less than 8%. These values indicate the sample size of 1770 patients is adequate for this endpoint.

	Assumptions with TIMI flow grade3 = 15% in in-hosp group		Assumptions with TIMI flow grade3 = 27% in in-hosp group	
Assumptions of relative difference (%) between the two groups	30	35	30	35
In-hosp group	15%	15%	27%	27%
Pre-hosp group	19.5%	20.3%	35.1%	36.5%
N per group with alpha=0.05	1106	826	512	376
N per group with alpha=0.025	1339	1001	620	456

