### **Statistical methods**

The primary objective of the study is to assess the efficacy of pre-hospital administration of ticagrelor compared to an in-hospital administration.

Two co-primary endpoints are considered relevant to assess this objective:

- The TIMI flow of the culprit artery at first angiography by the evaluation of percentage of patients reaching TIMI flow grade 3
- The ST-segment elevation resolution between pre-hospital assessment and in-hospital assessment pre PCI, by the evaluation of percentage of patients reaching a complete ST elevation resolution according to (Schröder R et al 1994) (ST resolution  $\geq 70\%$ ).

Each endpoint will be analyzed separately using a Chi-Square test. For each endpoint the null hypothesis is one of no difference between the two groups. The alternative hypothesis is that there is a difference. Correction procedure will be used to adjust for multiplicity while maintaining an overall Type I error rate of 5%.

Since, based on multiplicity procedure, the initial significance level is 2.5%, the sample size calculation will be based on a significance level of 2.5% and 80% power. Sample size calculations were derived using nQUERY7.

The sample size for the two co-primary endpoints is derived from the ST Resolution hypothesis. However, the study is enough powered for the 2 criteria when considering the table below.

The ST segment deviation was previously studied in On TIME2 study (Van't Hof Aw et al 2008), where complete ST resolution occurred in 20.7% of patients in the pre-hospital GP IIb/IIIa group versus 15.4% in the non GP IIb/IIIa group, all patients receiving a clopidogrel loading dose. This last number, corresponding to an in-hospital group was confirmed in Assent 4 PCI study where electrocardiographic reperfusion was shown in 14.9% of patients.

Based on this data, it is hypothesized that 15% of patients in the in-hospital group will achieve complete ST resolution versus 21% in the pre-hospital group (absolute difference of 6%). Taking into account a significance level of 2.5%, 779 evaluable patients are required in each treatment group to have 80% power using a two-group chi squared test of equal proportions. Assuming a 12% dropout for invaluable or missing ECG criteria, a total of 1770 patients are required to be enrolled in the study to assess the ST segment resolution difference.

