#### **12.2.1 Primary Efficacy Endpoints**

Each of the co-primary endpoint will be analyzed separately using a Chi-Square test.

The Holm multiple correction procedure will be used to maintain an overall Type I error rate of 5%. Specifically the two derived p-values will be compared. If the smaller p-value is greater than 0.025 then neither null hypothesis is rejected. Alternatively, if it is less than 0.025 then the associated null hypothesis is rejected and the null hypothesis associated with larger p-value is rejected if the p-value is less than 0.05.

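### Section 12.3 calls 1770 patients adequate for the TIMI 3 co-primary, but at the design alpha its own table needs more than 885 per group when the in-hospital rate is 15%

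*Protocol*

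**What the plan says.** Section 12.3 fixes the design basis: "the sample size calculation will be based on a significance level of 2.5% and 80% power". The 2.5% is the first Holm level. Section 12.2.1 states the rule: "If the smaller p-value is greater than 0.025 then neither null hypothesis is rejected". The larger p-value is tested at 0.05 only after the smaller one has led to rejection.

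The total of 1770 comes from ST-segment resolution (15% versus 21%, 779 evaluable per group, 12% dropout). TIMI 3 is then checked against that total. Section 12.3 gives a reported TIMI 3 range of 15–27% and says that clinicians regard a relative difference of 30 to 35% as relevant. It tabulates the number per group at the two ends of the range, for alpha 0.05 and in the row "N per group with alpha=0.025". On missing angiograms it says: "Dropout rate at initial angiography is assumed to be low, and less than 8"%.

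The text restricts the demonstrable difference to the hypotheses printed in bold, and then concludes: "These values indicate the sample size of 1770 patients is adequate for this endpoint". A second adequacy statement stands in both section 12.3 and the synopsis (Statistical methods): "However, the study is enough powered for the 2 criteria when considering the table below".

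**The concern.** Two of the four scenarios in the alpha 0.025 row need more patients per group than the trial randomises, before any angiogram is lost. The conclusion drawn from the table nevertheless declares the sample size adequate for the endpoint as a whole.

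TIMI 3 is one of two co-primary endpoints. If it is not significant and the in-hospital rate turns out near 15%, the result would be read against a stated adequacy that the design does not have there. A relative increase of the size that the protocol calls clinically relevant would be missed in roughly 29–44% of such trials (100 − 71 and 100 − 56). A reader who trusted the statement could take a null result as evidence against such an increase.

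**Working it through.** **Inputs.**
- Section 12.3: alpha 0.025, power 80%, two-group chi-square test, 1770 patients in total, angiography dropout below 8%, and the tabulated rates.
- The test is taken as two-sided because the synopsis says "The alternative hypothesis is that there is a difference", and because the two-sided formula returns the protocol's numbers.
- Per group: 1770 / 2 = 885 randomised. At the dropout bound, 885 × 0.92 = 814 evaluable.

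**Formula.** With in-hospital rate p1, pre-hospital rate p2 and mean rate p̄, let A = √[2p̄(1 − p̄)] and B = √[p1(1 − p1) + p2(1 − p2)].
- Number per group: n = (z₁ A + z₂ B)² / (p2 − p1)², with z₁ = 2.2414 for two-sided 0.025 (1.9600 for 0.05) and z₂ = 0.8416 for 80% power.
- Power at n per group: Φ{[(p2 − p1)√n − z₁ A] / B}.

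**Step 1: reproduce the protocol's figures.**
- ST resolution, 15% vs 21%: n = 778.1, so 779, as stated. Then 1558 / 0.88 = 1770.5, against 1770 stated.
- TIMI 3, 15% vs 19.5%: p̄ = 0.1725, A = 0.5343, B = 0.5334. n = (2.2414 × 0.5343 + 0.8416 × 0.5334)² / 0.045² = 1338.7, so 1339, as stated.
- The other alpha 0.025 entries also reproduce: 1001 (from the unrounded 20.25%; the printed 20.3% gives 983), 620 and 456. So do the alpha 0.05 entries: 1106, 826 (again from 20.25%), 512 and 376.

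The table is right. The question is whether the conclusion follows from it.

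**Step 2: compare with what is available, and compute power at alpha 0.025.** Example for 15% vs 19.5% with 814 per group: (0.045 × √814 − 2.2414 × 0.5343) / 0.5334 = 0.162, and Φ(0.162) = 56.4%.

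| In-hospital vs pre-hospital | Required per group | Power, 814 per group | Power, 885 per group |
|---|---|---|---|
| 15% vs 19.5% (+30%) | 1339 | 56% | 60% |
| 15% vs 20.3% (+35%) | 1001 | 71% | 75% |
| 27% vs 35.1% (+30%) | 620 | 90% | 93% |
| 27% vs 36.5% (+35%) | 456 | 97% | 98% |

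With 20.25% instead of 20.3%, the second row is 70.5% and 74.5%.

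**Step 3: between the two tabulated rates.** The protocol gives no entries here, so this is recomputation. With 814 per group and alpha 0.025, power first reaches 80% at an in-hospital rate of about 22% for +30% and about 18% for +35%. With 885 per group, the rates are about 21% and 17%.

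**Step 4: second Holm step (alpha 0.05, only if ST resolution is already significant), at 15%.**
- +30%: 1106 required; power 67% with 814 per group and 71% with 885.
- +35%: 826 required; power 79–80% with 814 and 83% with 885, depending on 20.25% or 20.3%.

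**The case against.** The best defence is that the protocol limits its own claim. It says that a difference can be shown for the cells in bold. The adequacy sentence in section 12.3 follows shortly after and refers to those values, and the other adequacy statement points to the table. The bold type is not visible in the text available here, so it may have marked only the adequate cells. The shortfall is also not hidden, since 1339 and 1001 are printed in the table, and the sample size is openly derived from ST resolution. This bears on how serious the lapse is. It does not rescue the wording: the concluding sentence speaks of the endpoint, not of selected cells.

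Two further points stand in part. First, 814 is a floor, because dropout is assumed to be below 8%. But both 15% cells at alpha 0.025 fail even at 885. Second, Holm can release alpha 0.05 for TIMI 3. That brings the +35% case at 15% to about 80%, but not the +30% case, and the protocol bases its calculation on 2.5%.

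Three stronger readings are tempting, and the documents do not support them:
- A reader might infer that the table itself shows a shortfall across the lower part of the 15–27% range. It has entries only at 15% and 27%. Anything between is recomputed, and its extent depends on the effect assumed.
- A reader might infer that the minimum detectable effect is misstated. The protocol states none; 30 to 35% is offered as clinically relevant.
- A reader might infer that the ST calculation is also wrong, because one cited study had 15.4% and 20.7%. The protocol presents its pair as a planning assumption ("it is hypothesized that 15% of patients in the in-hospital group will achieve complete ST elevation resolution versus 21% in the pre-hospital group"), and 779 is correct for it. The other cited in-hospital rate is 14.9%, and the cited contrast concerns a different drug class.

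**Conclusion.** The concern holds in limited form. At the design alpha of 0.025, the unqualified adequacy statements are contradicted by the protocol's own table when the in-hospital TIMI 3 rate is 15%: 1339 or 1001 required per group, against 885 randomised. Power there is about 56% and 71% at the dropout bound, or 60% and 75% with complete angiograms. At 27% the claim is sound.

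This rests on a two-sided chi-square test without continuity correction and equal groups, which reproduces the protocol's numbers, and on the 8% bound for the lower power figures. It does not depend on which cells were bold. The defect lies in the stated conclusion, not in the table, the test, the multiplicity rule or the ST-based sample size.

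**What to change.** Replace both adequacy statements in section 12.3, and the one in the synopsis, with the power that the design has. Suggested text:

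*With about 814 evaluable angiograms per group (8% dropout) and two-sided alpha 0.025, power for TIMI flow grade 3 is about 56% and 71% for relative increases of 30% and 35% from an in-hospital rate of 15%, and about 90% and 97% from 27%. Power of 80% requires an in-hospital rate of about 22% (30% increase) or 18% (35% increase). If ST resolution is already significant and TIMI 3 is tested at 0.05, power at 15% is about 67–71% and 79–83% for 814 to 885 evaluable per group. Of the tabulated scenarios at alpha 0.025, the sample size is adequate for those with an in-hospital rate of 27%.*

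The cost is a wording change in two places and a less favourable power statement. Enrolment, tests, alpha allocation and analysis sets stay as they are.
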